6. STUDY DESIGN

6.1 STUDY DESIGN

This is an active comparator, parallel group study in which subjects with burns meeting the study criteria will be randomly assigned to outpatient treatment with Santyl or bacitracin in a 1:1 ratio. Subjects who appear eligible will be presented with the study, and consent / assent will be obtained prior to any study procedures being conducted. The safety variables include adverse events and, specifically, burn wound infection or allergic contact dermatitis during treatment. Efficacy variables include time to complete healing and scar appearance. Both the Investigators and the subjects will contribute to these evaluations.

Enrolled, randomized subjects will be prescribed with test article (Santyl or bacitracin) and burn wound dressing supplies sufficient to last until burn wound has healed. Scar assessments will occur at 3 months and 6 months post burn healing.

Recruitment bias will exist, as any subject with a known contact dermatitis to bacitracin will be excluded. This will artificially reduce the number of allergic contact rashes in the bacitracin group, but the effect on the primary endpoint is unlikely to be significant. Study Procedure

For a summary of the required procedures by visit, refer to Table 12: Study Plan.

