7. STATISTICAL DESIGN

7.1 EVALUABILITY

All subjects who receive study medication will be evaluable for the safety analysis. All subjects who are randomized to receive study medication will be evaluable for the intent-to-treat analysis.

Unless specified otherwise, SPSS® Version 10.0 or higher will be utilized to perform the statistical analyses of efficacy and safety measures.

Categorical variables will be summarized in general using frequencies and percentages, whereas continuous variables will be summarized in general using descriptive statistics of number of observations (n), mean, standard deviation (SD), minimum (Min), median, and maximum (Max).

Hypothesis testing, unless otherwise indicated, will be performed at the 5% significance level. All P values will be rounded to four decimal places; P values less than 0.0001 will be presented as '<0.0001' in all tables. All group comparisons from analysis of variance (ANOVA) and/or analysis of covariance (ANCOVA) models will be based on Type III sums of squares. All confidence intervals will be two-sided with 95% coverage.

Missing or invalid data of efficacy assessments will be handled by individual scales or subscales on the basis of each individual assessment. Missing data for individual items will be assessed for each assessment of each scale and imputed with the mean score of the corresponding assessment and rounded up to the nearest integer if the number of items with missing data or invalid is less than or equal to 20% of total item number. Otherwise, the assessment score will be set to missing.

Considering that a subject's burn wound may be healed and/or a subject may discontinue from the study prior to the end of the study period, missing values at each weekly visit due to either burn wound healing or early termination or any other reasons will be imputed in this study prior to deriving the efficacy endpoints for evaluation, using the technique of last-observation carried forward (LOCF). By so doing, a burn wound that heals sooner will be given more weight for efficacy.

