7.1.1 Primary Efficacy

The primary objectives of the study include the proportion of subjects with the burn wound healed after 3 weeks of treatment, time (in weeks) to healing, and incidence of burn wound infection.,

Both the proportion of subjects with burn wound healed after 3 weeks of treatment and the time to heal between the two treatment groups will be analyzed using ANOVA. Also, the proportion of burn wounds healed at each of the 5 assessments (visit 2,3,4,5, and 6) between the two treatment groups will be analyzed through a mixed-effect ANOVA. The incidence of burn wound infection observed over the study will be compared between the two treatment groups, using a t-test.

The analysis of the primary efficacy evaluations will be performed for the ITT population.

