7.1.2 Secondary Efficacy

The secondary efficacy endpoint is to evaluate the effect of daily Collagenase Santyl ointment versus daily Bacitracin ointment on scar appearance at 90 days and at 180 days after the initiation of treatment. The secondary efficacy endpoint is defined as the VSS total score obtained at Visit 7 (Day 90) and at Visit 8 (Day 180).

The treatment effect of Collagenase Santyl ointment versus Bacitracin ointment on the VSS total scores will be obtained at each of the two post-healing assessment time points, using analysis of variance (ANOVA) for the ITT population. The mixed-effect model will utilize SPSSPROC MIXED to perform the analysis and define treatment (Santyl vs. Bacitracin) and assessment time point (4 visits: Visits 5, 6, 7 and 8) as well as their interaction as fixed effects, and subject as a random effect. The option of variance components will be used to define the covariance structure of the model.

In addition, a model-based t-test comparisons between Santyl vs. Bacitracin will be performed for each of the 2 assessment time points (or visits).

The null hypothesis states that there are no differences between the two treatments, with the alternative of non-zero differences. The type I error rate for rejecting a null hypothesis will be set at an alpha level of 0.05.

Prior to conducting the analysis, those VSS total scores that are obtained at the early termination visit will be assigned to the next scheduled study visit.

The analyses of the primary efficacy evaluations will also be performed for the PP population.

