8. SAMPLE SIZE JUSTIFICATION

A previous study of Santyl vs. white petrolatum in normal volunteers with dermatome wounds enrolled 28 subjects, each of whom served as their own control (paired wounds, treated differently). At 9 months follow-up, the Santyl treated wounds had lower total scores on the Vancouver Scar Scale, suggesting the efficacy of Santyl ointment, although the difference between Santyl and its petrolatum vehicle was not significant (P = 0.09, Wilcoxon signed-rank test).

The current study uses a parallel-group design and non-uniform injuries on different individuals, which are more likely to lead to a larger variance as compared to the previous study. The injuries are non-uniform and different in nature compared to the dermatome study. Assuming a moderate effect size of 0.750 for the present study, the sample size of 80 (40 per group) will yield a statistical power of approximately 70% to detect a difference between the two treatment groups at the significance level of 0.05 (2-sided). Based on a two-sample t-test, the current study is comparable in power to the described previous study.

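### The five-visit mixed-effect ANOVA on healed status has no stated link or covariance; with one common variance, its visit-by-visit comparisons would not hold the 5% level

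*Combined protocol and SAP*

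**What the plan says.** Section 7.1.1 plans two analyses that cover Day 21. The first is an ordinary ANOVA on the proportion healed after three weeks. The second is added to it: the proportion healed "at each of the 5 assessments (visit 2,3,4,5, and 6) between the two treatment groups will be analyzed through a mixed-effect ANOVA". Visits are weekly (6.2.2), so Visit 4 is Day 21. Section 7.1.1 gives no link function, covariance structure or definition of visit contrasts for the second analysis, and it does not say which analysis governs the Day 21 conclusion.

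The only mixed model described in detail is the one for the Vancouver Scar Scale in 7.1.2. It has treatment, visit and their interaction as fixed effects and subject as a random effect, and "The option of variance components will be used to define the covariance structure of the model". Model-based t-tests at individual visits are mentioned only there.

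On error level, 7.1 states: "Hypothesis testing, unless otherwise indicated, will be performed at the 5% significance level". Wounds must be open at Visit 1 (6.2.1). A subject whose wound closes skips the remaining weekly visits (6.2.2 and the study plan table in Section 12), and 7.1 fills missing weekly values by LOCF. A closed wound therefore stays closed in the analysis data.

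**The concern.** The variance of a 0/1 status is p(1-p). It is small when few or nearly all wounds have closed, and largest when about half have. Healing moves every subject from open towards closed, so this variance changes over Visits 2 to 6. A normal-theory mixed model with a random subject effect and one residual variance gives every visit the same total variance. It therefore understates the standard error at visits where healing is under way and overstates it at visits near 0% or 100%.

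The plan asks for a comparison at each visit, which is where such a model fails. The analysis stands under Primary Efficacy and one of its visits is the primary time point. A falsely significant visit contrast could therefore be reported as support for the primary result.

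**Working it through.** **Inputs from the documents.** There are 40 subjects per group (Section 8: "the sample size of 80 (40 per group) will yield a statistical power of approximately 70% to detect a difference"), 1:1 allocation (6.1), a 5% two-sided level (7.1 and Section 8), and five visits with closed status absorbing (6.2.2, 7.1). The plan states no error rate or standard error for this analysis, so there is no figure of its own to reproduce. The stated 70% power is a separate matter: its own inputs give about 91% by a two-sample t-test. It does not enter this check.

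**Inputs assumed.** The documents give no healed proportion at any visit. The curves below are assumptions, the same in both arms (no treatment effect), with complete data. The covariance (random subject, one residual variance) is inferred from 7.1.2.

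**Formula.** With balanced data and treatment-by-visit fixed effects, the estimated variance of the treatment contrast at any visit is (2/n) × the mean of the five within-arm variances. The correct value at visit j is (2/n) × p_j(1-p_j). Hence

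- SE ratio at visit j = sqrt(mean of p(1-p) / p_j(1-p_j))
- type I error at visit j ≈ 2 × [1 − Φ(1.96 × SE ratio)]

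**Worked example, 10/30/55/75/90% healed at Visits 2 to 6.** The variances are 0.09, 0.21, 0.2475, 0.1875 and 0.09. They sum to 0.825, so the mean is 0.165.

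| Visit | SE ratio | Closed-form error | Simulated, common variance | Simulated, own variance |
|---|---|---|---|---|
| 2 | 1.354 | 0.8% | 0.7% | 5.7% |
| 3 | 0.886 | 8.2% | 8.0% | 4.9% |
| 4 (Day 21) | 0.816 | 11.0% | 10.6% | 5.6% |
| 5 | 0.938 | 6.6% | 6.4% | 5.1% |
| 6 | 1.354 | 0.8% | 0.7% | 5.8% |

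**Range over other assumed curves** (20,000 simulated null trials each, Satterthwaite degrees of freedom):

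| Healed at Visits 2–6 (%) | Error at Visit 4 | Largest error at any visit |
|---|---|---|
| 2/15/50/85/98 | 20.1% | 20.1% (Visit 4) |
| 5/20/50/80/95 | 15.3% | 15.3% (Visit 4) |
| 5/30/60/85/95 | 13.8% | 13.8% (Visit 4) |
| 5/35/70/90/97 | 13.1% | 15.2% (Visit 3) |
| 2/10/30/60/80 | 11.0% | 13.2% (Visit 5) |
| 10/45/80/93/98 | 9.5% | 18.6% (Visit 3) |
| 10/30/50/65/75 | 9.0% | 9.0% (Visit 4) |
| 10/25/40/55/65 | 8.3% | 8.3% (Visits 4 and 5) |
| 15/60/85/95/98 | 6.5% | 18.6% (Visit 3) |
| 20/70/90/97/99 | 3.6% | 18.0% (Visit 3) |
| 40/75/93/98/99 | 1.2% | 20.0% (Visit 2) |
| 30/80/95/99/99.5 | 0.7% | 20.2% (Visit 2) |

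A REML fit of the mixed model to the 5/35/70/90/97% curve rejected at Day 21 in 12.7% of 150 simulated trials, in line with 13.1%. The range is illustrative and not a bound: a steeper Weibull-shaped curve reaches about 23% by the closed form.

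**What is not affected.** Over these 12 curves:

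- The Day 21 contrast on its own visit's variance gives 4.5% to 5.8%.
- The treatment main effect of the mixed model gives about 5%.
- The treatment-by-visit test gives 6.4% to 8.5% (6.2% for the worked example).

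The separate one-way ANOVA on Day 21 status, enumerated exactly at 40 per arm, gives 4.3% to 5.9% for true proportions of 0.30 to 0.95.

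**The case against.** The strongest reply has three parts.

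**The plan does not prescribe a common variance here.** This is correct. The variance-components option is stated for the scar scale only, and an unstructured covariance would remove the problem. But 7.1.1 does not specify one. A random-subject model is the ordinary reading of a mixed-effect ANOVA, and it is the only mixed model the document describes. The gap in specification leaves the defect open.

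**The primary Day 21 test is sound.** This is also correct, and it limits the point. A reader might infer that the Day 21 primary result carries two to three times its nominal error. The documents do not support that. The Day 21 proportion has its own ANOVA, which keeps roughly 5%. Section 3 lists open versus closed wounds among the exploratory endpoints. The five-visit model is an additional analysis, though 7.1.1 places it under Primary Efficacy without ranking the two.

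**The size depends on assumed healing curves.** This stands too. Section 2.1 says only that second-degree burns may take several weeks to heal. Even the direction of the error at Day 21 is unknown: the simulated contrast is anti-conservative with roughly 30% to 80% healed by then, and conservative with 90% or more. What does not depend on the choice is that every curve tried had at least one visit inflated to about 8% or more. Nor is every visit badly off: in the worked example Visit 5 is close to nominal.

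**Conclusion.** The concern holds in a limited form. Section 7.1.1 leaves the link and covariance of a five-visit model for a 0/1 outcome unstated. Under a common variance, the Day 21 contrast from that model has a type I error of about 1% to 20% depending on the healing curve (about 11% for 10/30/55/75/90%). The most inflated visit reaches about 8% to 20%, and visits near 0% or 100% healed have error well below 5%. The treatment-by-visit test is only mildly inflated, at about 6% to 8.5%.

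This rests on three assumptions: the covariance inferred from 7.1.2, healing curves that are not in the documents, and complete data at 40 per arm. The mechanism is certain under the first assumption; the size at any one visit is not. The damage is confined to visit-specific contrasts and does not extend to the separate Day 21 ANOVA or the model's treatment main effect. The plan should be changed, because the comparison it asks for at each visit is the part that such a model gets wrong.

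**What to change.** In 7.1.1, replace the five-visit mixed-effect ANOVA with a report, at each of Visits 2 to 6, of the proportion healed per group and the between-group difference, with a 95% confidence interval from that visit's own data (for example a score interval). State that the Day 21 inference comes from the single-visit comparison and that the other visits are descriptive.

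If a repeated-measures test is kept, specify a binary model, for example GEE with a logit link and robust standard errors, or a linear model with visit-specific variances. A logit model with treatment-by-visit terms may not be estimable at a visit where no or all wounds in a group are closed, which is a reason to prefer the descriptive report.

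The cost is a small change of SAP wording. The same weekly data are used and nothing new is collected. What is given up is a formal test at the visits other than Day 21.

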2.2 RATIONALE

Outpatient management of partial thickness burns normally involves the application of an ointment, which may contain an antibiotic. Concerns about the promotion of antibiotic resistant staphylococci, combined with known risks of allergic hypersensitivity reactions to certain topical antibiotics, support the exploration of alternative treatments. Bacitracin ointment has been compared against white petrolatum in the management of post-procedural wounds among 922 patients with 1249 wounds (17). No significant difference was observed in infection rates (2% in the petrolatum group vs. 0.9% in the bacitracin group) or healing rates. No patients in the white petrolatum group developed allergic contact dermatitis compared with 4 patients (0.9%) in the bacitracin group. In a separate study of 142 patients, 147 Mohs micrographic surgery wounds on the ear were postoperatively treated with either gentamicin ointment or petrolatum. No significant differences were seen between treatments in the incidence of suppurative chondritis infections (4.76% in the gentamicin group; 6.67% in the petrolatum group), whereas there was a higher incidence of inflammatory chondritis in the gentamicin group (11.90% vs. 3.33% for petrolatum) (18). In the 1990s, the North American Contact Dermatitis Group (NACDG) listed bacitracin among the top 10 allergens, based on skin testing. Approximately 9% of bacitracin tests were positive.

. Bacitracin ointment is selected for this study because it is a standard treatment used by the Investigators, and is widely used in burn care. A significant cost difference exists between bacitracin and other ointments, such as Collagenase Santyl. The therapeutic intent for this study is to see if there is a cost reduction benefit as well as reduction in healing time for two standard of care treatment options for partial thickness burn wounds.

This trial does not include a rigorous evaluation of local infection, as quantitative bacteriology from biopsied tissue would be required, nor does it include a rigorous evaluation of hypersensitivity reactions, as de-challenge / re-challenge or measurement of specific humoral and cellular immune responses would be required. Instead, the appearance of the wound bed and periwound tissue will be evaluated, with

particular attention to the description of any rashes. Clinically diagnosed infections may be treated, but use of topical treatment will require that the subject exit the trial.

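### Burn wound infection, a yes/no primary outcome, is compared by t-test with no provision for sparse or zero counts, and the documents give no infection rate for burns

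*Combined protocol and SAP*

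**What the plan says.** Section 7.1.1 lists three primary objectives: the proportion healed after 3 weeks, "time (in weeks) to healing, and incidence of burn wound infection". For the last of these: "The incidence of burn wound infection observed over the study will be compared between the two treatment groups, using a t-test". On the population: "The analysis of the primary efficacy evaluations will be performed for the ITT population". It does not say whether the t-test pools the variances, names no interval for the infection difference, and gives no alternative for few or no events.

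Section 7.1 has categorical variables summarized as counts and percentages and makes every confidence interval two-sided 95%. It names no test for categorical outcomes.

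On how common infection will be, the documents point two ways:
- Section 2.2 cites two studies, neither in burns. For post-procedural wounds: "No significant difference was observed in infection rates (2% in the petrolatum group vs. 0.9% in the bacitracin group"). For ear wounds after Mohs surgery it gives 4.76% with gentamicin and 6.67% with petrolatum.
- Section 9.5 places burn wound infection among the adverse events that are frequent in the trial's own population, without a figure.

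Section 6.1 also treats infection as a safety outcome: "The safety variables include adverse events and, specifically, burn wound infection or allergic contact dermatitis during treatment".

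**The concern.** A t-test takes its standard error from the observed spread. For a yes/no outcome that spread shrinks to nothing as events disappear. With no infection in either arm both sample variances are zero: the test cannot be computed, and an interval built the same way collapses to a point at zero. Subjects in that trial would still carry an unknown risk that 40 per arm cannot rule out.

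The trial sets an ointment without an antibiotic against an antibiotic, and infection is a primary objective. The reader needs to know how large an excess of infections remains possible. A missing p-value or a zero-width interval does not say. With small non-zero counts, the choice of test can also decide which side of 0.05 the result falls on, so it should be settled before the data are seen.

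**Working it through.** **Inputs.** 40 per arm (Section 8), two-sided alpha 0.05 (Section 8), two-sided 95% intervals (Section 7.1), and the two pairs of rates in Section 2.2. Assumed: all 40 per arm are analysed, each subject counts once as infected or not, nothing is missing, and variances are pooled. The pairs 5% vs 0.9%, 10% vs 2% and 15% vs 5% are also assumed, to show the range.

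**The plan's own figure.** The plan states no power or expected rate for infection. Its only power figure, about 70%, follows a discussion of scar scores ("Assuming a moderate effect size of 0.750 for the present study"). With 40 per arm the noncentrality is 0.75 × √(40/2) = 3.354 on 78 degrees of freedom, which gives 91.2%, so 70% is not reproduced. That is a separate matter and has no bearing on infection.

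**No event in either arm.** P = (1 − p1)^40 × (1 − p2)^40.
- 2% vs 0.9%: 0.98^40 × 0.991^40 = 0.446 × 0.697 = 0.310. Expected events in the whole trial: 40 × (0.02 + 0.009) = 1.16.
- Both arms at 2%: 0.98^80 = 0.199. Both at 0.9%: 0.991^80 = 0.485.
- 4.76% vs 6.67%: 0.009. Expected events: 40 × (0.0476 + 0.0667) = 4.57.
- Both arms at 5%: 0.017. Both at 10%: 0.0002.

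**What 0/40 allows.** The exact 95% upper limit is 1 − 0.025^(1/40) = 8.8%. For 0/40 vs 0/40 the Newcombe interval for the difference is −8.8 to +8.8 points. The Miettinen-Nurminen limit solves d/(1 − d) = (1.96²/40) × (80/79) = 0.0973, so d = 8.9 points. The t-based interval is 0 to 0.

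**Coverage of the t-based 95% interval**, by enumerating all 41 × 41 outcomes and counting a zero-width interval as reported:

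| True rates | Source | No event in either arm | Coverage |
|---|---|---|---|
| 2% vs 0.9% | Section 2.2, post-procedural wounds | 31.0% | 68.6% |
| 4.76% vs 6.67% | Section 2.2, ear surgery | 0.9% | 94.5% |
| 5% vs 0.9% | assumed | 9.0% | 86.9% |
| 10% vs 2% | assumed | 0.7% | 91.1% |
| 15% vs 5% | assumed | 0.02% | 94.7% |

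Newcombe coverage is 99.9% at 2% vs 0.9%, 99.7% at 5% vs 0.9%, 98.0% at 10% vs 2% and 96.9% at 15% vs 5%.

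**Leaving out the 0/0 trials.** At 2% vs 0.9%, 0.6862/(1 − 0.3104) = 99.5%. At 5% vs 0.9%, 0.869/(1 − 0.0895) = 95.4%. At 10% vs 2%, 0.911/(1 − 0.0066) = 91.7%. Only the last is a shortfall among trials where the test can be computed.

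**Type I error of the t-test.** 0.7% at a common rate of 2%, 4.3% at 5% and 5.9% at 10%. Fisher's exact test rejects in 0.01%, 0.4% and 1.7% of trials.

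**Where the choice of test matters.**
- 4/40 vs 0/40: pooled t p = 0.041, Welch t 0.044, Fisher 0.116.
- 5/40 vs 0/40: pooled t p = 0.021, Fisher 0.055.
- At true rates of 10% vs 2%, the pooled t-test and Fisher disagree at the 5% level in 23% of trials.

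**The case against.** The strongest reply is that the difficulty depends on rates the documents do not claim for burns. Section 9.5 calls burn wound infection frequent here, and at the second pair cited in Section 2.2 the t-test behaves well. This stands. A reader might infer that infection is rare in this trial and that the test will often fail. The documents do not support that: the low rates come from post-procedural wounds. Nor do they exclude it, because Section 9.5 gives no figure and its list serves the judgement of whether an event is related to treatment. The lower pair is the one that includes bacitracin, the comparator here.

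A second reply is that the 69% and 87% coverage figures come almost wholly from counting the 0/0 case as a reported interval that misses. That also stands. Section 7.1.1 names a test and no interval, and Section 7.1 would put 0/40 and 0/40 in front of the reader as counts. It would go too far to say that the plan will report certainty of no difference; it gives no usable inference in that case.

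A third tempting reading is that the t-test inflates false positives. It does not do so materially: the highest null rejection rate at the rates above is 5.9%.

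Finally, a reader might conclude from Section 6.1 that infection belongs with safety and that its p-value should be only descriptive. The synopsis, Section 3 and Section 7.1.1 all make it a primary objective. Changing that is a design decision for the sponsor, not a correction.

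**Conclusion.** The point holds as a conditional one. A binary primary outcome has a t-test and no rule for sparse data, in a plan that gives no infection rate for its own population. If rates were near 2% and 0.9%, about 3 trials in 10 of this size would have no computable test. At rates around 5% to 7% in both arms the t-test is adequate. At 10% vs 2%, an assumed pair, there is a modest loss of coverage, to 91%, that does not come from the 0/0 case.

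The sizes rest on 40 analysed per arm, one outcome per subject and no missing data. The recommendation does not depend on settling how frequent infection will be, because the replacement works at any of these rates.

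**What to change.** In Section 7.1.1, replace the t-test for infection with:
- the number of infected subjects per arm, each proportion with an exact 95% interval;
- the risk difference with a Miettinen-Nurminen or Newcombe 95% interval, one of them named in advance;
- a p-value from one prespecified test for binary data, for example an exact test.

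Add the infection rate expected in burns, with its source, or say that none is available. Keep infection as a primary objective unless the sponsor decides otherwise. Before finalizing, confirm that the chosen software returns the interval at 0/40 vs 0/40, since some score-interval routines fail there. Section 7.1 lets a program other than SPSS be specified.

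The cost is wording only, with no change to sample size, visits or data collection. Intervals will be wider at low counts. An exact test is also more conservative: 4/40 vs 0/40 moves from p = 0.041 to p = 0.116, and at true rates of 10% vs 5% rejection falls from 14.6% with the pooled t-test to 4.3% with Fisher. If that loss is unwelcome, a less conservative test for binary data can be named instead, provided it is fixed in advance and defined for zero counts.
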